1. ACTH will be initiated 2 weeks prior to the completion of the prednisone taper for patients who are receiving prednisone at the time of consent.
2. ACTH will be initiated 2 weeks prior to stopping preventive medications such as tacrolimus, cyclosporin, and mycophenolate.

Patients randomized to no treatment will be followed for up to 6 months or until disease relapse, whichever occurs first. Patients who relapse within 6 months will be given the option of reassignment to the ACTH treatment group after remission has been achieved using conventional corticosteroid therapy.

Patients randomized to ACTH treatment will be given ACTH for 12 months. During the second 6 months, the ACTH dose will be reduced to 50% of the starting dose. The outcome of interest is the presence of relapses after dose reduction. Follow-up will occur throughout the 12 months of therapy, and also for 6 months following the completion of ACTH therapy. The outcome of interest is the percentage of patients with relapses in the 6 months after completing a 12 month course of ACTH treatment.

Visits

Screening visit: The study will be explained to the patient and family. Inclusion and exclusion criteria will be reviewed to determine eligibility. Consent and assent will be obtained as appropriate. Medical history will be recorded. A physical exam will be performed. If indicated, a

plan for prednisone tapering will be explained to the family. The date of the baseline visit will either be determined at that visit or via telephone for patients who are currently in relapse.

Baseline visit: The patient will be seen and have baseline labs (renal function panel, cholesterol, urinalysis, urine protein/creatinine ratio). A urine pregnancy test will be performed in females of childbearing age (achieved menarche) who are randomized to ACTH treatment along with counseling in required birth control. An interval medical history and quality of life (QOL) survey will be performed. Patients will have a physical examination. Patients will be randomized to either ACTH gel or no treatment. Patients will be given Albutix and instructions for daily monitoring of the urine and recording the results. Patients randomized to ACTH gel will receive their first injection in clinic and be taught how to perform injections at home. A stop date for other immunosuppressive medications will be provided, if appropriate, 2 weeks after starting ACTH.

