ACTH Treatment ACTH will be dosed by body surface area (BSA), with an initial dose of 80U per 1.73m². After 6 months of treatment, the initial dose will be reduced by 50% (1st reduction), to complete the second 6 months of ACTH therapy.

If patients develop significant side effects on the initial dose, they will have an early dose reduction by 50% at the discretion of each individual site PI (1st reduction). They will complete a total 6 months of treatment with the initial and reduced dose. After 6 months, ACTH will be reduced again by 50% (2nd reduction), to complete the second 6 months of ACTH therapy.

Patients who do not tolerate ACTH therapy despite an early dose reduction will exit the study with reporting of adverse events as appropriate.

Patients who relapse on a reduced dose of ACTH during the second 6 months of treatment will have their dose reverted to the previous dose and complete a total of 12 months of treatment with no further dose reductions.

Patients with two relapses on the highest tolerated ACTH dose will exit the study.

| BSA | Initial Dose | 1st Reduction (50%) | 2nd Reduction (25%) |
|------------|---------------------|----------------------------|----------------------------|
| 0.50-0.60 | 24U = 0.3mL | 12U = 0.15mL | 8U = 0.1mL |
| 0.61-0.75 | 32U = 0.4mL | 16U = 0.2mL | 8U = 0.1mL |
| 0.76-0.95 | 40U = 0.5mL | 20U = 0.25mL | 12U = 0.15mL |
| 0.96-1.09 | 48U = 0.6mL | 24U = 0.3mL | 12U = 0.15mL |
| 1.10-1.25 | 56U = 0.7mL | 28U = 0.35mL | 16U = 0.2mL |
| 1.26-1.45 | 64U = 0.8mL | 32U = 0.4mL | 16U = 0.2mL |
| 1.46-1.60 | 72U = 0.9mL | 36U = 0.45mL | 20U = 0.25mL |
| ≥ 1.61 | 80U = 1.0mL | 40U = 0.5mL | 20U = 0.25mL |

*Note: there is rounding of the doses to the closest administrable amount by subcutaneous injection.

Interval Visits

Telephone contact will occur weekly for the first 3 weeks after randomization. This will include screening for adverse events, reviewing medications and timing of medication changes, review of Albustix testing, and reviewing dosing of ACTH if applicable. Patients randomized to ACTH treatment will have two additional telephone contacts one month after ACTH dose reduction or discontinuation. This is to screen for symptoms of adrenal insufficiency.

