Follow-up visits in patients randomized to ACTH will occur 1 month, 2 months, 4 months, 6 months, 8 months, 10 months, 12 months, 15 months and 18 months after the baseline visit. An interval medical history (including screening for adverse events) will be performed. Patients will have a physical examination. A renal function panel, cholesterol, urinalysis, urine protein/creatinine ratio, and QOL survey will be obtained at months 6 and 12. Urine pregnancy test, if applicable, will be obtained at months 4 and 8.

[figure not shown]
The dose of ACTH will be reduced by 50% after 6 months of treatment. Patients who have significant side effects attributed to ACTH will have an earlier dose reduction (i.e., before 6 months) at the discretion of each individual site PI. The PI will be asked to review possible side effects with the patient at each visit and decide if a dose reduction is warranted. A telephone contact will be made 1 month after dose reduction to screen for symptoms of adrenal insufficiency.

Relapses will be treated with prednisone, at 2mg/kg/day or 60mg/m²/day (maximum dose 60 mg) until remission is achieved, with a subsequent taper off therapy over 4 weeks. For patients receiving a reduced dose of ACTH, the dose will be reverted back to the last effective dosage on which remission was sustained, and continue at that dose until the end of the study. If >1 relapse occurs on the initial ACTH dose, ACTH therapy will be considered a failure and terminated.

The total ACTH therapy duration will be 12 months, after which, the subjects will be seen at follow-up at 15 and 18 months.

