Patients who are randomized to no treatment will have follow-up visits up to the time of relapse, at 1 month, 2 months, 4 months, and 6 months. An interval medical history (including screening for adverse events) will be performed. Patients will have a physical examination. A renal function panel, cholesterol, urinalysis, and urine protein/creatinine ratio, and QOL survey will be obtained at month 6. They will be treated with prednisone for any relapses and have the option to be placed on ACTH during the last 2 weeks of the prednisone taper if the relapse occurred within 6 months of the baseline visit. The subsequent visit schedule and procedures will be identical to the schedule for subjects initially randomized to ACTH (i.e., it will include a baseline visit, telephone contacts, and 18 months of follow-up). Alternatively, the patient may elect to be treated via standard of care in collaboration with the treating nephrologist, and the patient will then exit the study.

Flow Chart of Study Course

Participant Selection

Sixty subjects will be recruited from 10-12 large pediatric centers. Subjects may also be identified via physician or self-referral from advertisements placed on NephCure. Additionally, subjects may be recruited from registries of individuals interested in research participation.

Patients and their caregivers will be approached during a relapse of nephrotic syndrome or within 4 months of a relapse. The following criteria will be reviewed during the screening visit to determine eligibility:

Inclusion criteria

1. Age >1 year at onset of nephrotic syndrome
2. Age 2-20 years at time of randomization
3. Estimated GFR > 50 ml/min/1.73 m² at most recent measure prior to randomization (Schwartz formula)
4. Steroid responsive nephrotic syndrome throughout clinical course (never required a second agent to attain remission of a relapse of nephrotic syndrome)
5. History of frequently relapsing or steroid dependent nephrotic syndrome (defined as 2 or more relapses within 6 months after initial therapy or 4 or more relapses in any 12 month period OR relapse during taper or within 2 weeks of discontinuing prednisone).
6. Patient is currently in relapse of nephrotic syndrome or had a relapse within the last 4 months (defined as an increase in the first morning urine protein to creatinine ratio ≥ 2 or Albustix reading of ≥ 2 for 3 or 5 consecutive days).

Exclusion criteria

1. Prior treatment with ACTH.

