2. Cyclophosphamide or rituximab within the last 4 months.
3. Lactation, pregnancy, or refusal of birth control (abstinence qualifies) in females with child-bearing potential.
4. Planned treatment with live or live-attenuated vaccines once enrolled in the study.
5. Participation in another therapeutic trial concurrently or 30 days prior to randomization.
6. Active/serious infection (including, but not limited to Hepatitis B or C, HIV).
7. Malignancy concurrently or within the last 2 years.
8. Systolic or diastolic blood pressure >95% for age/height while receiving maximal doses of 3 or more medications.
9. Prior diagnosis of diabetes mellitus (Type I or II) or fasting glucose >200mg/dL
10. Organ transplantation
11. Contraindications to Acthar: scleroderma, osteoporosis, systemic fungal infections, ocular herpes simplex, recent surgery, history of or the presence of peptic ulcer, congestive heart failure, uncontrolled hypertension, primary adrenocortical insufficiency, or adrenal cortical hyperfunction
12. Secondary cause of nephrotic syndrome (e.g., SLE)
13. Biopsy demonstrating a diagnosis other than minimal change, FSGS or a variant (mesangial proliferation, IgM nephropathy)
14. Inability to consent/assent

Statistical Analysis

The primary end-point of the study and on which the statistical power is based is the proportion of patients who have a relapse in the 6 months following randomization to either ACTH or no ACTH.

We hypothesize that the 6 month relapse rate for patients receiving no treatment is 70%. In order to detect a 6 month relapse rate of 30% for patients receiving the ACTH gel, we will randomize 30 patients in each arm using a two sided z test with $\alpha=.05$. Our statistical power to detect such a difference is 91% which assumes two interim analyses at 50% and 100% of accumulated information. That is, once 30 patients have 6 month relapse data, we will conduct the first interim analysis. The last one will be completed once we have relapse data on all 60 patients. The table below gives the operating characteristics for such a design:

| Number of Patients with 6 Months Data | Boundary p-value |
|--|-------------------------|
| 30 | 0.006 |
| 60 | 0.045 |

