In addition to the completion of the appropriate forms, any serious adverse event or serious and unexpected suspected adverse reaction occurring during the study or in a post-study period of one month will be reported to the principal investigator, the Data Monitoring Committee (DMC), the local IRB, the sponsor, the study supporter, and participating sites within 2 business days. The IND sponsor will make an assessment of whether the event constitutes an unanticipated problem posing risks to subjects or others (UP). This assessment will be provided to the Emory University IRB, which, in turn will make a final determination. If the Emory IRB determines an event is a UP it will notify the appropriate regulatory agencies and institutional officials.

Adverse events that do not meet criteria for Serious Adverse Event will be reported using the Adverse Event Form during the follow up visit. Information regarding the diagnosis, date of occurrence, severity of the event, and therapy will be recorded. A determination of the relationship of the adverse event to the study participation will be made by the Participating Site investigator. Should a relationship be found, results will be reported to the sponsor, the study-supporter, and the DMC within 1 business week.

Data and Safety Monitoring Plan

An external Data Monitoring Committee (DMC) will be constituted prior to the randomization of the first patient. The DMC will consist of a minimum of three individuals outside the Division of Pediatric Nephrology. The individuals shall be practicing clinicians with experience in clinical research. At least one member will be a nephrologist, and two members will be pediatric subspecialists. Details on the membership, responsibilities and working procedures of the DMC will be described in the DMC Charter.

The DMC will perform the first safety review using a data cutoff 6 months after randomization of the first patient and every 6 months thereafter, unless otherwise requested by the Chairman of the DMC. The DMC will also receive reports on a regular basis on all SAEs reported for this trial. One interim analysis and one final analysis are planned. These analyses will coincide with the timing of the scheduled DMC meetings. Recruitment will not be interrupted unless otherwise requested by the Chairman of the DMC. Results of the DMC review will be shared with the PI and all participating sites within 1 business week.

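### A child who cannot tolerate ACTH despite an early dose reduction leaves the study with no stated relapse follow-up, so an exit before month 6 can leave the primary outcome missing

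*Combined protocol and SAP*

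**What the plan says.** **Exit rule.** Under ACTH Treatment: "Patients who do not tolerate ACTH therapy despite an early dose reduction will exit the study with reporting of adverse events as appropriate". This ends study participation as well as drug. The only thing it asks for afterwards is adverse event reporting.

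**Timing.** Under Interval Visits: "Patients who have significant side effects attributed to ACTH will have an earlier dose reduction (i.e., before 6 months"). The same section adds: "The PI will be asked to review possible side effects with the patient at each visit and decide if a dose reduction is warranted". Visits in the first half-year fall at months 1, 2, 4 and 6. Weekly calls in the first three weeks also screen for adverse events. Both the reduction and the exit can therefore come before month 6.

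**Contact after stopping.** Two calls follow a dose reduction or discontinuation. Their stated purpose is: "This is to screen for symptoms of adrenal insufficiency". Under Adverse Event Reporting, serious events are reported if "occurring during the study or in a post-study period of one month".

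**The other arm.** Under Study Design and Methods: "Patients randomized to no treatment will be followed for up to 6 months or until disease relapse, whichever occurs first". After a relapse, a child in this arm may move to ACTH or be "treated via standard of care in collaboration with the treating nephrologist, and the patient will then exit the study".

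**Endpoint and analysis.** Statistical Analysis defines the powered endpoint as the "proportion of patients who have a relapse in the 6 months following randomization to either ACTH or no ACTH". It compares the arms by a two-sided z test, analyses children in the arm assigned, and expects relapse data on all 60 at the final look. It has no rule for a missing six-month outcome and no allowance for one in the sample size.

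**The concern.** The endpoint is counted from randomization, but the exit rule stops observation when drug is stopped for intolerance. A child who exits relapse-free before month 6 has an unknown outcome, and the plan does not say whether that child is dropped, counted as relapse-free or counted as relapsed. Assigning children to their randomised arm does not settle this, because it names the arm and does not supply the outcome.

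The loss is also lopsided. The other written treatment exits come after a relapse, when the primary outcome is already known: the standard-of-care exit in the no-treatment arm and the exit or termination after repeated relapses on ACTH. Children who cross over from no treatment have already relapsed too. The missing outcomes created by the treatment and tolerability rules therefore all fall in the ACTH arm.

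At stake is a primary result that depends on an unwritten choice, made in an open-label trial when the data may already be known. Outcomes not collected at the time are hard to recover later.

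**Working it through.** **Inputs from Statistical Analysis.** 30 children per arm; relapse 70% without treatment and 30% on ACTH; boundary p-values 0.006 (30 children) and 0.045 (60 children); stated power 91%.

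**Assumptions.** The number and timing of exits, and the relapse risk after exit. The documents give none of these.

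**1. The plan's own figure.** For an unpooled z test, SE = √[(0.7×0.3 + 0.3×0.7)/30] = 0.118 and 0.40/0.118 = 3.38. With two looks at 0.006 and 0.045, power is 91.7%, which agrees with the stated 91%. It assumes all 60 outcomes are known.

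**2. Sample size alone.** Using only the final 0.045 look, unpooled power is 91.6% with 30 ACTH outcomes, 90.1% with 27 and 88.2% with 24. With pooled variance the figures are 88.4%, 86.5% and 84.2%. Lost numbers are a minor issue.

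**3. Bias from dropping exits, hazard unchanged.** Only children still relapse-free at exit lose their outcome. Those who relapsed earlier stay in as relapses. Assume 20% of the ACTH arm stops at month t, regardless of relapse, with a constant hazard giving 30% over 6 months. Risk before t is r = 1 − 0.70^(t/6), and the available-case rate is (0.80×0.30 + 0.20×r)/(0.80 + 0.20×r).

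- t = 2: r = 0.112, so 0.2624/0.8224 = 31.9%
- t = 3: r = 0.163, so 0.2727/0.8327 = 32.7%
- t = 4: r = 0.212, so 0.2823/0.8423 = 33.5%

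The true rate is 30%, so the error works against ACTH.

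**4. Same stopping, higher risk afterwards.** Assume that after exit the hazard is the one that gives 70% over 6 months. The risk left is s = 1 − 0.30^((6−t)/6) = 0.552, 0.452 or 0.331 for t = 2, 3 or 4. The true rate is 0.80×0.30 + 0.20×[r + (1−r)×s] = 36.0%, 34.8% or 33.4%. The available-case rates in step 3 are unchanged, so dropping exits favours ACTH by 4.1 points at month 2, 2.1 at month 3 and about nothing at month 4. The direction depends on assumptions that the documents do not supply.

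**5. Effect on the test.** Pooled two-sided z test, control 21/30, boundary 0.045:

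| ACTH scenario | exits counted relapse-free | exits dropped | exits counted as relapses |
|---|---|---|---|
| 7 relapses in 24 completers, 6 exits | 7/30, p = 0.0003 | 7/24, p = 0.003 | 13/30, p = 0.037 |
| 9 recorded relapses, 5 exits | 9/30, p = 0.0019 | 9/25, p = 0.012 | 14/30, p = 0.067 |
| 12 recorded relapses, 2 exits | 12/30, p = 0.020 | 12/28, p = 0.037 | 14/30, p = 0.067 |

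Example for 14/30: pooled proportion 35/60 = 0.583; SE = √(0.583×0.417×2/30) = 0.127; z = (0.700 − 0.467)/0.127 = 1.83; p = 0.067.

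The first row is the planned effect (7/24 = 29%), and every handling stays inside the boundary. The second row needs five exits who all relapse. In the third row the handling of two children decides significance.

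**The case against.** The best defence is that follow-up is already intended. The visit schedule is written for patients randomized to ACTH, with no exception for those who stop, and the plan expects data on all 60 and an analysis by assigned arm. This stands in part: the schedule and the exit rule must at least be reconciled. But the schedule does not say that visits continue after an exit, and the more specific rule says the child leaves. The flow chart was not in the text available here and should be checked for a different rule.

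Three further points have force:

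- Withdrawal can lose outcomes in either arm, and so can revoked authorization, after which the protocol mentions only safety follow-up (Data confidentiality). The asymmetry belongs to the treatment and tolerability rules and not to all missing data.
- Hypotheses and End-points words the same endpoint as relapse in the first half-year on treatment. That differs from the randomization-based wording and should be reconciled. Under either wording, a child who stops early has no stated handling.
- Kaplan-Meier estimation would censor such a child, but the plan uses it for aim 2 and not for the primary test.

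Some stronger readings are tempting but unsupported:

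- A reader might infer that the rule biases the trial in favour of ACTH. Steps 3 and 4 show that either direction is possible.
- Exits unrelated to relapse might seem harmless. Step 3 shows that dropping them still biases the rate.
- The visit dates might suggest that at most four of the six months go unobserved (reduction at month 1, exit at month 2). That is not a bound, because the early weekly calls also screen for side effects and reduction is at site discretion.
- The two-exit row might be read as the chance that the trial result flips. It is one constructed outcome, and the documents give no basis for such a probability.

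**Conclusion.** The concern holds in this form. Followed as written, the exit rule for intolerance despite an early dose reduction loses the primary outcome of any child who leaves relapse-free before month 6. The plan does not say how that outcome is counted. Among the treatment and tolerability exits, only this one can precede the primary outcome, and it affects only the ACTH arm.

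The size is unknown because no exit rate or timing is given. If a fifth of the arm stops between months 2 and 4, dropping the relapse-free exits shifts the ACTH rate by about 2 to 3.5 points against ACTH under an unchanged hazard. Under the higher assumed hazard after stopping, the error ranges from 4.1 points in favour of ACTH at month 2 to about nothing at month 4. A result at the planned effect survives six exits under either extreme. A weaker result can turn on two children. The documents do not support saying that the trial's conclusion is likely to be wrong. They do support fixing a cheap and avoidable gap before outcomes are lost.

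**What to change.** **ACTH Treatment and Interval Visits.** Separate stopping ACTH from leaving the study. A child who stops ACTH keeps the daily Albustix record and the visits already scheduled, or telephone contact for relapse, to at least month 6, and is analysed in the randomised arm. This is outcome follow-up only; the clinical criteria for stopping drug stay as they are. State in the visit schedule that it applies after drug is stopped.

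**Statistical Analysis.** Prespecify how outcomes still missing in either arm enter the primary z test, at the interim and final looks. Report both extremes (all missing relapsed, none relapsed) as sensitivity analyses. Use one wording of the primary endpoint throughout.

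**Cost.** Changes of wording, plus dipstick records and planned contacts for a few children after they stop drug. Counting their time off drug may make the estimated ACTH effect slightly smaller.

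### For a child cut early to 50% ACTH who then relapses before month 6, two protocol sections give different doses, and the reversion rule has no tolerability cap

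*Combined protocol and SAP*

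**What the plan says.** The rules sit in two sections of the combined protocol and SAP.

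**ACTH Treatment.** A child with significant side effects may be cut to 50% of the initial dose before month 6, at the site PI's discretion. For that child, "After 6 months, ACTH will be reduced again by 50% (2nd reduction), to complete the second 6 months of ACTH therapy". No exception for relapse is attached. The section's one reversion rule is limited in time: "Patients who relapse on a reduced dose of ACTH during the second 6 months of treatment will have their dose reverted" to the previous dose, with no further reductions. On tolerability: "Patients who do not tolerate ACTH therapy despite an early dose reduction will exit the study with reporting of adverse events". On failure: "Patients with two relapses on the highest tolerated ACTH dose will exit the study".

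**Interval Visits.** This section also describes the early cut. After a relapse, a child on a reduced dose has it "reverted back to the last effective dosage on which remission was sustained, and continue at that dose until the end of the study". No month is named and tolerability is not mentioned. There is a general safeguard: "The PI will be asked to review possible side effects with the patient at each visit and decide if a dose reduction is warranted". On failure: "If >1 relapse occurs on the initial ACTH dose, ACTH therapy will be considered a failure and terminated".

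Control children who take ACTH as rescue follow the same schedule and procedures as those randomized to ACTH, so the same rules apply to them.

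**The concern.** An early cut for side effects is a planned pathway with its own column in the dose table, so a relapse on it should have one answer. For a relapse before month 6 the text points two ways. One section lowers the dose again at month 6, shortly after a relapse. The other raises or holds it, and can restore the very dose that was cut for side effects. Neither is attractive in a child who has both relapsed and reacted to the drug, and sites could treat the same child differently.

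The stake is mainly dosing and safety. The analytic reach is narrow:

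- Hypothesis 2 is touched only if the second-six-month relapse-free proportion is counted separately. In the Kaplan-Meier analysis read as time to first relapse, the child already has the event.
- Hypothesis 3 starts from completion of one year of ACTH, so the stopping rule helps decide who enters it.
- Leaving the study at a second relapse truncates the 12-month prednisone total and may truncate the 6-month relapse count.

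**Working it through.** **1. The scenario, side by side.** Assume BSA 1.0 m², initial dose 48U cut to 24U at month 3 for side effects, remission sustained on 48U, and relapse at month 5.

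| | ACTH Treatment | Interval Visits |
|---|---|---|
| Dose from relapse to month 6 | 24U (no reversion rule before month 6) | 48U |
| Dose in months 7-12 | 12U (2nd reduction) | 48U, held |
| Tolerability limit on the dose | not reached, as the dose falls | none stated |

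**2. Size of the dose gap.** The inputs are the dose table; its last row, for example, reads "80U = 1.0mL | 40U = 0.5mL | 20U = 0.25mL". The nominal ratio of initial dose to 2nd reduction is 100% / 25% = 4. With the table's rounded doses:

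| BSA (m²) | Initial / 2nd reduction | 1st / 2nd reduction |
|---|---|---|
| 0.50-0.60 | 24/8 = 3.0 | 12/8 = 1.5 |
| 0.61-0.75 | 32/8 = 4.0 | 16/8 = 2.0 |
| 0.76-0.95 | 40/12 = 3.3 | 20/12 = 1.7 |
| 0.96-1.09 | 48/12 = 4.0 | 24/12 = 2.0 |
| 1.10-1.25 | 56/16 = 3.5 | 28/16 = 1.8 |
| 1.26-1.45 | 64/16 = 4.0 | 32/16 = 2.0 |
| 1.46-1.60 | 72/20 = 3.6 | 36/20 = 1.8 |
| ≥ 1.61 | 80/20 = 4.0 | 40/20 = 2.0 |

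The middle column is the literal gap: 3.0 to 4.0, and exactly 4.0 in four of eight rows. It applies only where the initial dose was the last effective one. The right column is the gap if a site caps the reversion at the tolerated 50% dose and holds it there: 1.5 to 2.0. An unwritten cap therefore narrows the disagreement but does not remove it.

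**3. Where the sections agree.** An early-cut child who holds remission on 50% and then relapses on 25% goes back to 50% under both. A child never cut early who relapses on 50% in the second six months normally goes back to the initial dose under both.

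**4. The failure rules.** For a child never cut early, the highest tolerated dose is the initial dose, so both rules trigger on the same relapses. They come apart only when 50% is the highest tolerated dose and two relapses occur on it: the ACTH Treatment rule is met, while the Interval Visits rule is silent. The stated consequences also differ (leaving the study; stopping ACTH), but one does not exclude the other.

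**5. The primary comparison.** The plan states 91% power for 70% versus 30% with 30 per arm. For a fixed design with unpooled variance, SE = √[(0.7×0.3 + 0.3×0.7)/30] = √(0.42/30) = 0.118, and 0.40/0.118 − 1.96 ≈ 1.42, giving 92.2%. With two looks at 0.006 and 0.045 it is 91.7%; simulation with a pooled z test gives 89.7%. The plan's figure is reproduced. The end-point is any relapse in six months, so it is met at the first relapse, before either dose rule acts. The power does not depend on this point.

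**The case against.** The strongest reply is that the ACTH Treatment section simply leaves a gap and the Interval Visits section fills it. The month-6 halving describes the routine course, and that section's own relapse rule already cancels later cuts, so a relapse overriding the schedule fits the plan's logic. This is a reasonable reading, but no text available here says which section prevails. It is also the reading that carries the uncapped reversion. Some figures, including the study flow chart, are not available, so it cannot be excluded that one of them settles the order.

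Several stronger readings are tempting and are not supported:

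- *The protocol requires re-exposure to a harmful dose.* It does so only on a literal reading, and only where the initial dose was the last to sustain remission. The site PI reviews side effects at every visit, and intolerant children leave. What stands is that neither safeguard limits the dose to which a child is reverted.
- *The two failure rules contradict each other.* They do not. The ACTH Treatment rule is the broader one, and the Interval Visits rule does not claim to be the only ground for stopping. A literal reversion to the initial dose would also move a child's second relapse onto that dose, so two relapses on 50% need a different path. One example is a relapse on 25%, return to 50%, then two more relapses.
- *Up to 51 children are affected.* The figure 30 + 0.70 × 30 = 51 counts everyone the ACTH rules could govern at the plan's rates, if all 21 relapsing controls accept rescue. The inconsistency concerns early-cut children only.
- *The inconsistency causes missed visits.* Those follow from the exit rule in the ACTH Treatment section alone, and would remain if the two sections were merely aligned.

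The limited effect on Hypothesis 3 is also fairly argued. Children who fail on the initial dose do not complete a year of ACTH under either section; only early-cut children failing on 50% could differ. The prednisone comparison is already disturbed by control-arm rescue and exits.

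**Conclusion.** The point stands for one defined path: an early cut to 50% for side effects, followed by a relapse before month 6. Read as written, the two sections give months 7-12 doses that differ 3.0- to 4.0-fold if the initial dose was the last effective one, and 1.5- to 2.0-fold if a site caps the reversion at 50%. The failure rules need the same wording but are not in conflict. How many children would be affected cannot be computed, because the plan gives neither an early-reduction rate nor a second-relapse rate. Hypothesis 1 and the stated power are not affected. The change should be made for clear and safe dosing; the primary analysis does not need it.

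**What to change.** Put one rule in both sections, for randomized and rescue children alike.

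(a) On relapse at a reduced dose, at any month, revert to the last effective dose but never above the highest tolerated dose, with no later scheduled reduction. In the example above, the child stays on 24U to month 12.

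(b) Use the ACTH Treatment criterion, two relapses on the highest tolerated dose, as the failure rule in both sections. For a child never reduced for side effects, that dose is the initial dose.

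(c) As a separate improvement, not needed to reconcile the text: on failure, stop ACTH but keep the scheduled visits to month 18 and record relapses and prednisone. Leaving the study at the second relapse would then no longer cut short the ACTH arm's 12-month prednisone and relapse data.

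Items (a) and (b) cost one paragraph of protocol text. Item (c) costs the remaining visits for children who fail. Of the nine scheduled (months 1, 2, 4, 6, 8, 10, 12, 15, 18), 6, 5 or 4 remain after failure at the month 4, 6 or 8 visit. No extra patients or new procedures are needed.
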